6.1.6 Safety Variables

6.1.6.1 Adverse Events

An adverse event is the development of an undesirable medical condition or the deterioration of a pre-existing medical condition following or during exposure to a pharmaceutical product, whether or not considered causally related to the product.

Adverse Events will be collected from randomization throughout the treatment period up to and including the End-of-Treatment visit.

Serious adverse events (SAEs) will be recorded from the time of informed consent.

The following variables will be collected for each Adverse Event (AE):

- AE diagnosis/description
- The date and time when the AE started and stopped
- Intensity as measure of severity (Mild, Moderate, Severe)
- Whether the AE is serious or not

AstraZeneca AB D3250C00030 Final 2.0 04/Aug/2017

- Causality to IMP (Investigational Medical Product)
- Action taken with regard to investigational product (Dose Not Changed, Dose Increased, Dose Reduced, Drug Interruption, Drug Permanently Discontinued, Not Applicable)
- AE caused subject's withdrawal from study (yes or no)
- Outcome (Recovered/Resolved, Recovering/Resolving, Recovered/Resolved with Sequelae, Not Recovered/Not Resolved, Fatal)
- Whether the AE was associated with device malfunction

Additional variables will be collected for all SAEs including treatment given for the event.

6.1.6.2 Clinical Laboratory Tests

Hematology, Serum Clinical Chemistry and Urinalysis

Safety laboratory parameters as shown in Table 3 will be measured at the following visits: Screening, Day -1, 8, 29 and 57.

Table 3	Clinical Laboratory Tests		
Hematolog	y		
White blood	cell (WBC) count	Lymphocytes absolute count	
Hemoglobin	(Hb)	Monocytes absolute count	
Platelets		Eosinophils absolute count	
Neutrophils a	absolute count	Basophils absolute count	
Serum Clini	cal Chemistry		
Sodium		Alkaline phosphatase (ALP)	
Potassium		Alanine aminotransferase (ALT)	
Urea		Aspartate aminotransferase (AST)	
Creatinine		Gamma glutamyl transpeptidase (GGT)	
Albumin		Total bilirubin	
Calcium			
Glucose(fasti	ng)		
C-reactive pr	rotein (CRP)		
T4 ¹			
Thyroid-stim	ulating hormone (TSH) ¹	Follicle-stimulating hormone (FSH) (post-menopausal women only) 1	

Table 5	Clinical Laboratory Tests
Urinalysis	
Glucose	
Protein	
Blood	
Microscopy Red blood co Granular, Hy	(if positive for protein or blood): ell (RBC), WBC, Casts (Cellular, yaline)
¹ At Screening	g only.

Table 3Clinical Laboratory Tests

6.1.6.3 Vital Signs

Vital signs will be measured at the following time points: Screening, Day -1, Day 1 Pre-dose and 2 h post-dose, Days 2, 4, 5, 6, 8, 15, 29, 43 and 57.

The following vital signs measurements will be obtained:

- Systolic blood pressure (mmHg)
- Diastolic blood pressure (mmHg)
- Pulse rate (beats per minute [bpm])
- Oral body temperature (degree Celsius)

6.1.6.4 Electrocardiograms

An Electrocardiogram (ECG) will be performed at the following visits: Screening, Day 1, 29 and 57.

The ECG will be evaluated by the Investigator as normal or abnormal. If abnormal, it will be further documented as to whether or not the abnormality is clinically significant by the Investigator. For all abnormalities (regardless of clinical significance) the specific type and nature of the abnormality will be documented.

6.1.6.5 Physical Examination

The complete physical examinations will include an assessment of the general appearance, respiratory, cardiovascular, abdomen, skin, head, and neck (including ears, eyes, nose and throat), lymph nodes, thyroid, musculoskeletal and neurological systems. The complete exam will be performed at visit: Screening, Days 8, 29 and 57.

Statistical Analysis Plan

The brief physical examinations will include an assessment of the general appearance, skin, abdomen, cardiovascular system and respiratory. The brief exam will be performed on Day -1.

6.1.7 Eligibility Variables

Viral serology and drugs of abuse, alcohol will be assessed for eligibility. These results will not be listed in the CSR.

Follicle-stimulating hormone (females only) and serum pregnancy testing (females only) will be assessed and reported at screening.

Urine pregnancy testing will be performed at the following time points: Day -1 and Day 57

Table 4Pregnancy Testing (Female Subjects Only)

Beta human chorionic gonadotropin (beta-hCG)

Human chorionic gonadotropin (hCG) urine test (dipstick)

6.2 Analysis Populations

6.2.1 Randomized subjects

Randomized subjects include all subjects who pass screening and are randomized to a treatment (device) and an injection site.

6.2.2 Safety Analysis Set

The safety analysis set is a subset of the randomized subjects consisting of all subjects in the randomized set who received benralizumab.

Unless otherwise stated all listings except for PK concentration listing will be presented on the safety analysis set. Presentation of all data tabulations and figures except for PK data will also be on the safety analysis set, unless otherwise stated.

6.2.3 Pharmacokinetic Analysis Set

All subjects who received benralizumab and from whom PK blood samples are assumed not to be affected by factors such as protocol violations (e.g., disallowed medications or incomplete dose administration) and who had at least one quantifiable serum PK observation post first dose will be included in the PK analysis dataset. All PK tabulations and figures will be based on the PK analysis set.

Statistical Analysis Plan

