### Number of Subjects Planned

A total of 180 healthy subjects will be randomized to ensure at least 162 evaluable subjects at the end of the treatment period.

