### **7.5.3. Discontinuation Individual Stopping Criteria and Withdrawal from the Study**

Subjects will be discontinued from the study in the following situations:

- Healthy subject decision. The healthy subject is at any time free to discontinue treatment, without prejudice to further treatment.
- Severe noncompliance to study protocol.
- Any significant and clinically relevant changes in the safety parameters (e.g., ECG, BP, pulse rate, laboratory assessments and AEs).
- Study specific withdrawal criteria: If a subject reports symptoms, which are considered unacceptable by the subject or the Investigator, he/she will be withdrawn from the study. In particular:
  - Any other severe or serious adverse event (SAE) that is judged as possibly related to the IMP by the Investigator
  - Any case of Potential Hy's Law (PHL) according to [Appendix 15.3](#)

The appropriate AE form in the case report form (CRF) is to be completed.

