### **11.2. General Statistical Methodology**

The analysis of all endpoints will include all data captured during the study, unless the subject withdraws consent from study participation, regardless of whether study treatment is prematurely discontinued or delayed, and/or irrespective of protocol adherence.

Summary data will be presented in tabular format by treatment groups. Categorical data will be summarized by the number and percentage of subjects in each category. Continuous variables for parametric data will be summarized by descriptive statistics including n, mean, standard deviation, median, minimum value and maximum value (unless stated otherwise) for non-PK data. For PK data, in addition, geometric mean and coefficient of variation (CV%) based on log-transformed data will be presented.

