ALT	Alanine aminotransferase
ANOVA	Analysis of variance
APFS	Accessorized pre-filled syringe device
AST	Aspartate aminotransferase
AUC	Area under the concentration-time curve
AUC _{inf}	Area under the concentration-time curve from time zero extrapolated to infinity
AUC _{last}	Area under the concentration-time curve from time zero to the last observed time point
BLQ	Below the lower limit of quantification
BMI	Body Mass Index
CI	Confidence interval
CL/F	Apparent extravascular clearance
C _{max}	Maximum observed concentration
CRF	Case Report Form
CRP	C-reactive protein
CSP	Clinical Study Protocol
CV	Coefficient of variation
DRM	Data review meeting
ECG	Electrocardiogram
FSH	Follicle-stimulating hormone
GGT	Gamma glutamyl transpeptidase
Hb	Hemoglobin
IMP	Investigational Medical Product

ABBREVIATION AND ACRONYM LIST

Statistical Analysis Plan

Abbreviation / Acronym	Definition / Expansion
LLOQ	Lower limit of quantification
LS	Least square
MedDRA	Medical Dictionary for Regulatory Activities
NA	Not applicable
NC	Not calculated
NCA	Non-compartmental analysis
ND	Not determined
NR	No result
PDS	protocol deviation specification
РК	Pharmacokinetic
Q1	25 th percentile
Q3	75 th percentile
QCD	Quantitative Clinical Development
RBC	Red blood cell
SAE	Serious adverse event
SAP	Statistical Analysis Plan
SC	Subcutaneous
SD	Standard deviation
SOC	System Organ Class
t½	Terminal half-life
TEAE	Treatment-emergent adverse event
TLFs	Tables, Listings and Figures
T _{max}	Time when the maximum concentration is observed
TOST	Two one-sided tests
TSH	Thyroid-stimulating hormone
V _z /F	Apparent volume of distribution based on the terminal phase
WBC	White blood cell
$\lambda_{z,}$ Lamda Z	First order rate constant associated with the terminal (log-linear) elimination phase
%AUCextra	Percentage of AUC obtained by extrapolation

AMENDMENT HISTORY

Date	Version change	Brief description of change
26 June 2017	Final 1.0 to Draft 6.0	• Remove Physical Examination appendix based on protocol amendment 1. Abnormal results at baseline will be included as part of Medical History and abnormal results post baseline will be included as AEs. As a result, physical examination will not be listed by body system for each subject and each time point.
		• PK vendor change from MedImmune to PXL QCD
		• Add summary tables for both PK concentration and PK parameters by injection site and weight category

STATISTICAL ANALYSIS PLAN

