6.1.4.1 Pharmacokinetic Parameter Calculation Methods

The PK analyses of the serum concentration data for benralizumab will be performed by PXL Quantitative Clinical Development (QCD).

Non-compartmental PK analysis (NCA) will be performed using Phoenix WinNonlin (version 6.3, or higher, Certara, Princeton, New Jersey), in accordance with PXL SOPs.

PK analysis will, where possible, be carried out using actual sampling times recorded in the raw data. If actual times are missing, nominal times will be used. A non-compartmental approach consistent with the route of administration will be used for parameter estimation.

PK parameters will be estimated according to the following guidelines:

- C_{max} and T_{max} will be obtained directly from the concentration-time data.
- AUC_{last} will be estimated using the linear/log trapezoidal method.
- AUC_{inf} will be estimated as the sum of corresponding AUC_{last} and $C_{last}/\lambda z$ values:

$$AUC_{inf} = AUC_{last} + \frac{C_{last}}{\lambda_z}$$

- CL/F will be calculated as: $CL/F = \frac{\text{Dose}}{\text{AUC}_{inf}}$
- V_z/F will be calculated as: $Vz/F = \frac{CL/F}{\lambda_z}$

• Terminal half-life (t_{1/2}) will be calculated as: $t_{1/2} = \frac{\ln(2)}{\lambda_z}$, where λ_z is the first-order terminal rate constant estimated via linear regression of the terminal log-linear decay phase.

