6.3.9.3 Statistical Analysis of Pharmacokinetic Data

Primary PK analysis

The primary objective is to compare AUC_{inf}, AUC_{last} and C_{max} between APFS and AI devices following single SC administration of benralizumab. The analysis of variance (ANOVA) model will be employed on the log-transformed AUC_{inf}, AUC_{last} and C_{max}, separately, with fixed effects of treatment (device), body weight group and injection site in order to provide a descriptive comparison of the PK exposure between the 2 devices.

The estimated treatment (device) differences and the 90% CI (2-sided) on the log scale will be back-transformed to obtain the geometric mean ratios of AI to APFS and its corresponding 90% CI. The tables will also include the geometric least square means with 95% CI [Table 14.2.3.1]. Supporting statistical output for the analysis of PK parameters documented in Appendix 16.1.9.2.1.

The following SAS code will be applied, with AI sorted before APFS:

proc mixed data = <data>;

class <treatment_device> <weight category> <injection site>;

model <log_var> = <treatment_device> <weight category> <injection site>;

lsmeans <treatment_device> / cl alpha = 0.05;

```
estimate "AI versus APFS" <treatment_device> 1 -1 / cl alpha = 0.10;
```

run;

quit;

Secondary PK analysis

For T_{max} , a nonparametric analysis may be performed, based on evaluation during the blind data review.

To evaluate the PK of benralizumab administered to various anatomical injection sites and weight category, the PK parameters will be summarized by treatment (device) and injection sites [Table 14.2.2.3], and body weight categories [Table 14.2.2.2].

Furthermore, the ANOVA model of the primary analysis with the addition of the interaction term treatment (device)-by-injection site will be presented [Table 14.2.3.2]. The estimated differences of pairwise comparison between injection site within each treatment (device) and the corresponding 90% CI (2-sided) on the log scale will be back-transformed to obtain the geometric mean ratios of abdomen/arm, thigh/arm and thigh/abdomen and their corresponding 90% CIs.

Supporting statistical output for the analysis of PK parameters documented in Appendix 16.1.9.2.2.

The following SAS code will be applied:

proc mixed data = <data>;

class <treatment_device> <weight category> <injection site>;

model <log_var> = <treatment_device> <weight category> <injection site>
 <treatment_device> * <injection site>;

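### The PK set admits a subject with one quantifiable sample and AUClast has no minimum follow-up, so by default a very early leaver enters the primary AUClast ANOVA with a truncated value

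*SAP*

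**What the plan says.** - **Analysis set.** SAP 6.2.3, like Protocol 11.3.2, takes dosed subjects whose samples are assumed unaffected by factors such as protocol violations and "who had at least one quantifiable serum PK observation post first dose will be included in the PK analysis dataset". All PK tables and figures use this set.
- **AUClast.** The SAP abbreviation list defines it as "Area under the concentration-time curve from time zero to the last observed time point", and SAP Table 2 agrees. SAP 6.1.4.1 says that it "will be estimated using the linear/log trapezoidal method". Neither gives a minimum last day, a minimum number of points or a common end time.
- **Primary analysis.** SAP 6.3.9.3: "The analysis of variance (ANOVA) model will be employed on the log-transformed AUC_{inf}, AUC_{last} and C_{max}, separately", with device, weight group and injection site as fixed effects, giving an AI/APFS ratio with a 90% CI. The protocol names only AUC and Cmax.
- **Sampling.** Pre-dose on Day 1, then Days 2, 4, 5, 6, 8, 15, 29, 43 and 57. SAP 6.3.3 imputes nothing beyond AE dates and values below quantification.
- **Sizing.** The protocol synopsis randomizes 180 "to ensure at least 162 evaluable subjects at the end of the treatment period". The PK set definition does not apply that end-of-period condition.
- **Possible exclusions.** Protocol 11.2 states: "The analysis of all endpoints will include all data captured during the study, unless the subject withdraws consent from study participation". SAP 6.3.6 sends protocol deviations, including PK time window deviations, to a data review meeting that defines the analysis sets.

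**The concern.** AUClast measures exposure on a common footing only if subjects are followed for about the same time. A value cut off after a day or two mainly reflects when sampling stopped. On the log scale it is an extreme low outlier, so it does two things at once: it pulls down the geometric mean of its device, and it inflates the residual variance that sets the CI width for both devices. The reported AI/APFS ratio can then move away from 1, with a wider interval, although the devices deliver the same exposure.

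The exits most exposed to this are loss to follow-up and discontinuation under Protocol 7.5.3 for "Any significant and clinically relevant changes in the safety parameters". Protocol 11.2 addresses only consent withdrawal. Severe noncompliance, also listed in 7.5.3, could plausibly be handled as a protocol deviation. The study is open-label (Protocol 8.10), so without a stated rule any exclusion would be decided case by case with the device known.

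**Working it through.** **1. The plan's own sample size.** Inputs from Protocol 11.4 and SAP 4: CV 50%, limits 0.80-1.25, two one-sided tests at 5%, 80% power. Log SD = sqrt(ln(1 + 0.5²)) = 0.4724. The true ratio is not stated.
- At a true ratio of 1, exact TOST power needs 78 per group (156). Rounding up to complete sets of the 18 design cells gives 162. Power at 81 per group is 82.3%.
- True ratios of 1.01 and 1.02 need 158 and 160. So 162 is reproduced to within rounding.
- 162 / 0.9 = 180. At 90 per group, power is 87%.

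**2. How much AUC a truncated profile keeps.** This needs assumptions: a one-compartment SC profile, C(t) proportional to ka/(ka − ke) × (e^(−ke·t) − e^(−ka·t)), sampled at elapsed days 0, 1, 3, 4, 5, 7, 14, 28, 42 and 56, with the linear/log trapezoid.

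Example: absorption half-life 2 days and elimination half-life 15 days give ka = ln 2/2 = 0.347 and ke = ln 2/15 = 0.0462 per day. The Day 2 concentration is 0.286, so AUC to Day 2 = 0.5 × (0 + 0.286) × 1 = 0.143. AUC is 1.025 to Day 4, 3.795 to Day 8 and 19.57 to Day 57.

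| Last sample | Share of Day 57 AUC, example | Share, ka 0.1-1.0 per day and half-life 10-25 days |
|---|---|---|
| Day 2 | 0.143/19.57 = 0.7% | 0.2-2% |
| Day 4 | 1.025/19.57 = 5.2% | 2-12% |
| Day 8 | 3.795/19.57 = 19% | 7-34% |
| Day 29 | 75% | 54-86% |
| Day 43 | 91% | 81-96% |

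**3. Effect of one AI leaver in the SAP ANOVA.** 90 per device, six model parameters, 174 residual df, true ratio 1, share f from the example.
- Shift in log ratio = ln(f)/90.
- Residual variance ≈ 0.4724² + (ln f)² × (1 − 6/180)/174.
- CI half-width = 1.654 × SD × sqrt(2/90).

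At CV 50%:

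| Leaver | ln f | Ratio | Residual SD | Half-width (log) |
|---|---|---|---|---|
| None | – | 1.00 | 0.472 | 0.116 |
| Day 2 | −4.92 | 0.947 | 0.598 | 0.147 |
| Day 4 | −2.95 | 0.968 | 0.521 | 0.128 |
| Day 8 | −1.64 | 0.982 | 0.488 | 0.120 |

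Hand check for Day 2. The limits are ±ln 1.25 = ±0.2231, so the estimate must lie within ±(0.2231 − 0.1474) = ±0.0757. Its mean is −0.0547 and its SD is 0.4724 × sqrt(2/90) = 0.0704. The z-values are −0.30 and 1.85, so the chance is about 0.97 − 0.38 = 0.59.

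Simulated chance that the 90% CI lies in 0.80-1.25 (separate runs agree to about one point):

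| Leaver | CV 50% | CV 40% | CV 30% |
|---|---|---|---|
| None | 87% | 97-98% | 100% |
| Day 2 | 58-59% | 73-74% | 88-89% |
| Day 4 | 77-78% | 92% | 99% |
| Day 8 | 84-85% | 96% | 100% |

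The Day 2 result depends on the absorption assumption. With absorption half-lives of 1 to 3.5 days it is 51-68 / 63-84 / 79-96%.

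**4. Several leavers.** Dropout timing is a further assumption. Results are at CV 50/40/30%, absorption half-life 2 days, elimination half-life 10-20 days.
- Three per device, uniform over calendar time: 74-79 / 89-92 / 96-98%.
- Nine per device (the whole 10% allowance), same timing: 53-63 / 66-77 / 79-87%.
- Nine per device, all last sampled on Day 15 or later: 83-86 / 95-97 / 100%.

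**5. The other two parameters.** AUCinf needs a terminal slope (SAP 6.1.4.1), so it would usually be missing for a very early leaver. For Cmax, one AI Day 2 leaver at CV 50% gives a chance of 84-87% and a ratio of 0.99. From Day 8 on, Cmax is complete under these profiles.

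**The case against.** The strongest reply is that entry is a default, not a certainty. Parameters are derived only where possible, under vendor SOPs that are not in the documents. Deviation criteria sit in a separate specification, also not shown. The review meeting defines the analysis sets before database lock, and the SAP plans separate listings of excluded subjects and excluded data, so record-level exclusion is foreseen. All of this stands. The gap is shown for the SAP text, not for every procedure of the trial. It does not close the gap, because none of the visible text sets a follow-up criterion.

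A second reply is that no decision depends on the result. The SAP calls the comparison descriptive, the study is not a formal bioequivalence study, and 0.80-1.25 appears only in the sizing. AUCinf and Cmax are reported alongside, and listings and box plots would show the low values. This also stands and limits the severity. But a visible outlier still sits inside the reported AUClast ratio and interval.

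A reader might also infer that any subject lost in the first week does material harm. The calculation does not support that: a single Day 8 leaver costs little. Nor do the documents support a fixed percentage of lost AUC, because they give no absorption rate or half-life. They also say nothing about how often very early loss would follow one supervised dose in the unit.

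**Conclusion.** The point holds in limited form. Followed literally, the SAP puts truncated AUClast values into the primary ANOVA unless an exclusion route with no stated follow-up criterion removes them. Under the assumed profile, material harm from a single leaver is confined to last samples on about Day 2 to Day 4. At CV 50% the chance of meeting the sizing target falls from about 87% to about 58% (Day 2) or 78% (Day 4). At CV 40%, only the Day 2 case falls below 80%. One leaver on Day 8 costs about 2 to 3 points at the stated maximum CV and less otherwise; later exits cost less still. Several early leavers add up, but their number and timing are assumptions.

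Only AUClast is materially affected, and there is no formal test. Severity is minor to should-fix: the effect is narrow, but it falls on a named primary-analysis parameter and is cheap to prevent.

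**What to change.** In SAP 6.1.4.1 and 6.3.9.3, before concentrations are reviewed by device, adopt one of two rules:

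1. Use AUC from time 0 to a common day in the ANOVA, set to missing for a subject with no sample, quantifiable or BLQ, at or after that day.
2. Let AUClast enter the primary ANOVA only if a sample, quantifiable or BLQ, was taken on or after a stated day, for example Day 29 or Day 43.

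Under either rule, list truncated profiles by device, keep the all-subjects AUClast ANOVA as a sensitivity analysis, and say how missed intermediate visits are handled. State how the consent-withdrawal wording in Protocol 11.2 applies. If the deviation specification or vendor SOPs already hold a minimum-profile rule, write it into the SAP.

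The exact day matters little. With nine dropouts per device, uniform over calendar time, a rule at Day 15, 29 or 43 gives 81-83, 84-85 or 82-85% at CV 50%. With a Day 43 rule, the single Day 2 leaver no longer matters (87% at CV 50%, ratio 1.00).

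The cost is SAP wording and one extra ANOVA run. A few dosed subjects leave the AUClast ANOVA, which the sizing allows for. If all 18 dropouts were removed, 180 − 18 = 162 remain. With calendar-uniform timing, a Day 43 rule keeps about 162 + 18 × 14/56 = 166.5, and a Day 29 rule about 162 + 18 × 28/56 = 171. Exclusions for other reasons would come on top. No visits, samples or subjects are added.

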6.3 Statistical Analysis Methods

6.3.1 Listings and Descriptive Statistics

All listings will include stratification factors (weight group and injection site). All summary tables will be presented by treatment (device), unless stated otherwise.

Demographic (Age, Sex, Race and Ethnicity) and baseline characteristics data will be summarized separately by treatment (device) and overall.

Pharmacokinetic data will be summarized separately by treatment (device) only and by treatment (device), body weight and injection site.

Adverse Events will be listed for each subject and summarized by System Organ Class and Preferred Term assigned to the event by Medical Dictionary for Regulatory Activities (MedDRA) Version 19.1.

Medical and surgical history will listed for each subject by System Organ Class and Preferred Term assigned to the event or history by MedDRA.

Prior and concomitant medication will listed for each subject by preferred drug name and medication as reported coded to preferred drug name using the World Health Organization Drug Dictionary Enhanced Plus Herbal (September 2016).

Frequency counts (number of subjects [n] and percentages) will be made for each qualitative variable. Descriptive statistics (n, Mean, Standard Deviation [SD], Median, Minimum and Maximum) will be calculated for each quantitative variable (unless otherwise stated). Descriptive statistics will only be presented if $n \ge 3$. For PK data, geometric mean, geometric mean +/- SD and coefficient of variation (CV%) based on log-transformed data will be presented.

Unless otherwise stated rules for decimal places are as follows:

- n and N the population total are always given as whole numbers,
- Ratios 2 decimal places,
- All measured data will be listed with the same number of decimal places or significant figures (with same precision) as the original raw data, with the exception of data for which the original number of decimals exceeds four decimal places; in these cases the data will be presented to three significant figures,
- An extra digit of precision will be added (typically four significant digits in total) for reporting of the geometric least-squares (LS) means and bounds of all confidence intervals within inferential analyses,

• A maximum of three decimal places will apply to all summary statistics.

The following rules will apply to any repeated safety assessments occurring within the treatment period:

- If the repeated measurement of a specific parameter occurs prior to IMP administration (Day 1), then the last obtained value prior to dosing will be used in the descriptive statistics and in the calculation of changes from baseline;
- If the repeated measurement of a specific parameter occurs after IMP administration (Day 1), then the first (non-missing) value after dosing relative to the scheduled time-point will be used in descriptive statistics and in the calculation of changes from baseline.

For safety assessments performed at Screening, if the repeated assessment occurs at Screening the last available value will be used in the summary statistics.

